3 STUDY IMPLEMENTATION

3.1 STUDY DESIGN

This is a multi-center, two-stage, phase 2 study.

Subjects with newly diagnosed moderate or severe chronic GvHD according to the NIH criteria, who need systemic therapy, will be started on ibrutinib as a continuous daily dose of 420 mg by mouth. Treatment will continue in cycles consistent of 28 days on outpatient basis.

Participants with response at 6 months (CR+PR) will continue therapy until 12 months.

Participants who have a perception of benefit from ibrutinib therapy may continue on ibrutinib past the 12-month timepoint, based also on investigator discretion and discussion for up to 24 months.

Subjects may continue on stable doses of their immunosuppressive medications with the intent to taper it. See Section [4.1](#).

Addition of any systemic immunosuppressive therapy aimed at controlling chronic GvHD symptoms is prohibited and will be considered treatment failure. Participants in need of additional systemic immunosuppressive therapy will be taken off ibrutinib treatment.

Subjects may remain on topical therapy for chronic GvHD (See Section [4.2](#)).

Abbreviated Title: Ibrutinib for Chronic GvHD

Version Date: 4/26/2023

One steroid pulse (i.e., prednisone equivalent of 0.5-2 mg/kg/day) is allowed (See Section [4.1.2](#)).

Up to 28 evaluable subjects will be enrolled and treated for up to 24 months. Enrollment will occur in 2 stages: in the first stage 14 subjects will be enrolled, and if ≥ 4 subjects have a response (CR+PR at 6 months) the accrual will continue until a total of at least 25 evaluable subjects have been enrolled. As it may take 3 to 6 months to determine if a subject has experienced a response, a temporary pause in the accrual may be necessary to ensure that enrollment to the second stage is warranted.

Evaluation of chronic GvHD diagnosis per NIH criteria ([Appendix A](#)) and Chronic GvHD Organ Specific Staging and Global Scoring ([Appendix D](#) and [Appendix E](#)) will be performed at screening. Chronic GvHD Organ Specific Staging and Global Scoring ([Appendix D](#) and [Appendix E](#)) evaluations will be repeated at 9 months and 12 months, and every 3 months until off treatment.

Chronic GvHD Activity Assessment (Clinician) Form A ([Appendix F](#)) will occur at baseline, at 6 weeks and then 3, 6, 9 and 12 months from the start of ibrutinib by the bone marrow transplant physician and/or nurse practitioner trained in chronic GvHD assessments.

[figure not shown]

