3.2 DRUG ADMINISTRATION

For this study we will use an ibrutinib dose of 420 mg (3 x 140 mg capsules) taken once a day on every day of every cycle.

Ibrutinib capsules should be swallowed whole and should not be broken, chewed or opened. Each dose of ibrutinib should be taken at approximately same time each day with 8 ounces (approximately 240 mL) of water. If a dose of ibrutinib is missed, it should be taken as soon as possible on the same day. If it is missed for the entire day, it should not be made up.

Missing < 20% doses in the first six months is allowed. Treatment with ibrutinib will be discontinued if the subject has missed ≥ 20% doses in the first six months of the study.

Participants will be asked to keep a medication diary ([Appendix I](#)). The first dose will be delivered in the clinic on Day 1, after which subsequent dosing is typically on an outpatient basis. Ibrutinib will be dispensed to subjects in bottles at each visit. Unused ibrutinib dispensed during previous visits must be returned to the site and drug accountability records updated at each visit. Returned capsules must not be redispensed to anyone.

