Treatment with ibrutinib will be discontinued if because of unacceptable toxicity the subject has missed drug for more than a total of 28 days in the first six months of the study.

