3.8.1 Criteria for removal from protocol therapy

- Completion of 6-month course of protocol therapy and no response (PR or CR)
- Chronic GvHD progression by NIH criteria and/or primary physician determination
- Unacceptable toxicity that requires the subject to be off study drug for more than 28 consecutive days in the first six months of the study
- Noncompliance with study medication (defined as missed >20% doses in the first six months of the study for the reason of noncompliance)
- If ibrutinib becomes unavailable
- Principal Investigator discretion
- Participant requested to be withdrawn from active therapy
- Recurrence of underlying malignancy
- Subject becomes pregnant

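### The toxicity stopping limit is 28 days in total in one section and 28 consecutive days in another, and it is unclear which interruptions the 20% missed-dose rule counts

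*Combined protocol and SAP*

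**What the plan says.** Three places in the protocol govern interrupted dosing in the first six months.

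- **End of Section 3.3.2.3 (the sentence after Table 1).** Treatment stops for unacceptable toxicity once "the subject has missed drug for more than a total of 28 days in the first six months of the study". The count is cumulative. The sentence follows the hepatic table, but its wording is general.
- **Section 3.8.1, toxicity criterion.** "Unacceptable toxicity that requires the subject to be off study drug for more than 28 consecutive days in the first six months of the study". The count is of one unbroken run.
- **Section 3.2.** "Missing < 20% doses in the first six months is allowed", and then "Treatment with ibrutinib will be discontinued if the subject has missed ≥ 20% doses in the first six months of the study". No reason for the missed doses is stated.
- **Section 3.8.1, noncompliance criterion.** Defined as "missed >20% doses in the first six months of the study for the reason of noncompliance". The reason is stated, and the inequality is strict.

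Section 3.8.1 also lists principal investigator discretion as a ground for removal. No section gives an order of precedence.

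**The concern.** The two toxicity rules share their trigger, their window and their consequence, and differ only in how days are counted. A participant with several shorter holds can be over one limit and not the other. The dose-modification tables in Section 3.3.2 provide for hold-and-restart more than once, so separate holds are foreseen by the protocol itself.

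The 20% rules add a second, weaker uncertainty. If Section 3.2 counts every missed dose, it reaches toxicity holds and the holds that the protocol itself directs (Section 4.6 for procedures, Section 3.2.1 for a short course of a strong CYP3A inhibitor). If it is about adherence, as in Section 3.8.1, it does not.

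All these rules act before the 6-month response assessment (C7D1). Which one is applied could affect whether a participant is still on drug at that visit. After discontinuation the post-treatment phase begins (Section 3.1), and the telephone follow-up in Section 3.5 does not list chronic GvHD response scoring among the data collected. A site that continues treatment on the strength of Section 3.8.1 may also depart from Section 3.3.2.3, which would be a deviation as Section 8.7 defines it.

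**Working it through.** **Inputs.** Cycles last 28 days (Section 3.1: "Treatment will continue in cycles consistent of 28 days on outpatient basis"). Dosing is once daily (Section 3.2), so a missed day is a missed dose. The 6-month visit is C7D1 (Section 5.1.1), which follows six cycles: 6 × 28 = 168 doses. The protocol does not fix this denominator, so 180, 182 and 183 days are shown as alternatives.

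**Step 1: put the limits on one scale.** The toxicity limit is 28/D and the 20% line is 0.20 × D. The last column assumes that Section 3.2 counts toxicity days.

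| D | 28/D | 0.20 × D | First whole count at 20% or more | Totals caught by 3.3.2.3 alone (no run over 28) |
|---|---|---|---|---|
| 168 | 16.7% | 33.6 | 34 | 29–33 |
| 180 | 15.6% | 36.0 | 36 | 29–35 |
| 182 | 15.4% | 36.4 | 37 | 29–36 |
| 183 | 15.3% | 36.6 | 37 | 29–36 |

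On 168 doses, 29 to 33 days is 17.3% to 19.6% (29/168 to 33/168). If Section 3.2 is instead an adherence rule, the gap between 3.3.2.3 and 3.8.1 has no upper end at 33.

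**Step 2: apply each rule to the same history (D = 168).**

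| History | 3.3.2.3 closing rule | 3.8.1 missed-dose criteria | 3.2, any-reason reading |
|---|---|---|---|
| Two 15-day toxicity holds: 30 days, 30/168 = 17.9% | stop | not met (longest run 15) | below 20%, permitted |
| Two 20-day toxicity holds: 40 days, 40/168 = 23.8% | stop | not met (longest run 20) | stop |
| One 29-day toxicity hold: 29/168 = 17.3% | stop | met | below 20%, permitted |
| 38 doses held for procedures or similar, longest run 14: 38/168 = 22.6% | does not apply | not met (neither toxicity nor noncompliance) | stop |

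The first row is enough to show the main conflict. The last row shows the scope question only.

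**Step 3: the inequality sign.** On 168 doses, 33.6 is not a whole number. Both forms of the 20% rule therefore first act at 34, and the sign changes nothing. It matters only where 20% is a whole number: 36 of 180 missed through noncompliance meets Section 3.2 but not Section 3.8.1.

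**Step 4: is any design figure affected?** The plan gives no figure for interrupted dosing. The two-stage design in Section 10.2 reproduces:

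- Early termination at p = 0.20 is the sum over x = 0 to 3 of b(x; 14, 0.20) = 0.698 (stated 69.8%).
- P(success | p) is the sum over x = 4 to 14 of b(x; 14, p) × P(Y ≥ 8 − x), with Y binomial(11, p). It is 0.0933 at p = 0.20 and 0.9026 at p = 0.45, within the stated 0.10 limits.

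None of this changes with the stopping rule as such.

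**Step 5: scale of a conditional effect.** This rests on an assumption that is not in the documents: a share of would-be responders is removed under these rules and counted as non-responders. With shares of 4%, 8% and 12% the effective rate is 0.45 × 0.96 = 0.432, 0.45 × 0.92 = 0.414 and 0.45 × 0.88 = 0.396. Power falls from 90.3% to 87.1%, 83.3% and 78.8%. These are illustrations, not estimates.

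**The case against.** The strongest reply is that the rules can all be obeyed at once. Section 3.8.1 is a list of grounds for removal. It does not say that they are the only grounds, it never instructs a site to continue, and it includes investigator discretion. Sections 3.2 and 3.3.2.3 each mandate discontinuation, so a site applying everything stops at the earliest trigger. This stands in part: a reader might infer that Section 3.8.1 obliges a site to keep a participant on drug, and the text does not support that. But the earliest-trigger reading leaves the word consecutive in Section 3.8.1 with no work to do, no section states it, and Section 3.2 expressly permits missing less than 20%.

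Second, the 20% rule in Section 3.2 follows directly on instructions about a dose the participant forgets, and can be read as an adherence rule matching Section 3.8.1. That is fair. A reader might infer a flat contradiction between the two 20% rules; the documents support only an unclear scope. The vocabulary does not settle it: procedure holds are described as held, but the toxicity rule in Section 3.3.2.3 speaks of missed drug.

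Third, a reader might infer that repeated toxicity holds have no cumulative limit. That is true only of Section 3.8.1 read alone, and the dose tables also cap the number of episodes. Nor do the documents show that cumulative holds are the usual pattern, since they give no frequency or duration. Reaching 34 doses through procedures and short interruptions alone would take several such events within six months.

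Fourth, few sites are named, and the research team discusses each participant weekly (Section 7.5.1). That makes divergent practice less likely, but it does not tell the team which limit applies.

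**Conclusion.** The concern holds as an internal inconsistency that should be fixed. The total and consecutive limits for the same toxicity trigger are both in current text and give different answers. On 168 doses, and counting toxicity days under Section 3.2, the totals stopped by Section 3.3.2.3 alone are 29 to 33 days with no run over 28. The scope of the 20% rule is a secondary ambiguity, and its sign has no effect on that denominator.

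A reader might go further and infer that the primary CR+PR count depends on which section a site follows. The documents do not establish that. The effect depends on two separate matters:

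- **How removed participants are classed.** Section 6.3.1 expressly makes early progressors evaluable and is silent on removal for missed doses. Section 10.4.2 uses evaluable participants, and Section 10.3 describes those with at least one dose.
- **Whether an earlier response counts.** Section 10.1.1 refers to response at 6 months; Section 10.2 says at or before 6 months.

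The cut-offs (3 versus 4 of 14, 7 versus 8 of 25) mean that one participant could matter. Nothing in the documents says how many would be affected. The sample size is not in error.

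**What to change.** The sponsor should reconcile Section 3.2, the closing sentence of Section 3.3.2.3 and Section 3.8.1 so that they carry, in identical wording:

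1. one toxicity-interruption rule, stating whether days are counted in total or consecutively;
2. one missed-dose rule, with a single threshold and sign, stating whether the reason matters;
3. one denominator of scheduled doses for the first six months;
4. a statement of whether toxicity holds and protocol-directed holds (Sections 3.2.1 and 4.6) count as missed doses.

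Which rule to adopt is for the sponsor. The amendment should also state the 6-month endpoint status of a participant removed under either rule, so that the conditional effect described above is closed off.

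The cost is a wording amendment in three places plus one sentence on endpoint status. The medication diary and drug accountability records needed to apply the rules are already collected, and the sample size does not change.

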3.4 PARTICIPANT SELF-ASSESSMENTS (ENGLISH SPEAKING SUBJECTS ONLY)

Participant self-report questionnaires administered in this study are part of the standard NIH chronic consensus recommended criteria for the evaluation of chronic GvHD in clinical trials. These standardized assessments are designed to evaluate participant quality of life and symptoms. Questionnaires will include Lee Symptom Scale, SF36 form and the NIH Form B-Chronic GvHD Activity Assessment-Patient Self Report ([Appendix G](#)). The purpose of these evaluations is to assess the potential benefit of the administered therapy as compared to the baseline. These forms have been extensively used, published and validated. These forms are also standard part of many NCI CCR chronic GvHD protocols. In a recent study median time for persons to complete these forms was 15 minutes (range 8-22 minutes). See the Study Calendar in [Appendix K](#) for timepoints of participant self-assessments.

3.5 POST-TREATMENT EVALUATIONS

All participants after last dose will be then followed by a phone call to the participant and/or the primary physician's office at 12 and 24 months after starting the first dose of ibrutinib. The phone call will focus on collecting data: a) survival status and primary and contributing cause of death if pertinent, b) ongoing systemic treatment for chronic GvHD, need to systemic therapy change (including what type) and systemic therapy discontinuation (including date), c) primary malignancy progression, d) any second primary malignancy (including type), e) return to work or school part-time or full-time. This information will be recorded in the CRF and the participant's medical record.

3.6 STUDY CALENDAR

The study calendar can be found in [Appendix K](#).

3.6.1 Telehealth

Telemedicine is the use of interactive audio, video, audio-visual, or other telecommunications or electronic technology by a licensed health care practitioner to deliver clinical services. This protocol will allow the team to practice telemedicine to communicate with participants in real time, to be able to monitor and collect data, as well as the ability to share the participants' health information with other health professionals. Providers may include primary providers, specialists/consultants and nurses. Other members of the healthcare team may also be present to aid with the communication devices, scheduling or records management. These remote visits

may include the following: patient history, verbal exam, symptom reporting, education, and questionnaires.

Telemedicine visits will be scheduled using site-approved remote platforms. Telemedicine visits may be used for follow-up visits if deemed appropriate by the PI. All telemedicine visits must be documented in the patient's medical record like a normal onsite visit and the note should indicate that this visit was performed virtually.

Remote visits will be conducted in compliance with site guidelines and FDA regulations.

3.6.2 Local Evaluations

A patient may be asked to come to the NIH CC or Washington University for an in-person assessment or be referred to their local provider, if clinically indicated, and at the discretion of the investigator. All physical exams, assessments, labs, and imaging used for follow-up or restaging visits may also be performed with the patient's local physician as determined by the PI. For in-person assessments, physical examinations may be omitted at the discretion of the investigator. For laboratory evaluations conducted with local providers, interlaboratory variability is not a concern. In the case of any visits with participants' local providers, records will be obtained for the research records.

3.7 COST AND COMPENSATION

3.7.1 Costs

3.7.1.1 NIH

NIH does not bill health insurance companies or participants for any research or related clinical care that participants receive at the NIH Clinical Center. If some tests and procedures performed outside the NIH Clinical Center, participants may have to pay for these costs if they are not covered by insurance company. Medicines that are not part of the study treatment will not be provided or paid for by the NIH Clinical Center.

3.7.1.2 Participating Sites

Subjects costs will be based on local guidelines as described in the site-specific consent.

3.7.2 Compensation

Participants will not be compensated on this study.

3.7.3 Reimbursement

3.7.3.1 NIH

The NCI will cover the costs of some expenses associated with protocol participation. Some of these costs may be paid directly by the NIH and some may be reimbursed to the participant/guardian as appropriate. The amount and form of these payments are determined by the NCI Travel and Lodging Reimbursement Policy.

3.7.3.2 Participating Sites

Reimbursement will be provided per local guidelines.

3.8 CRITERIA FOR REMOVAL FROM PROTOCOL THERAPY AND OFF STUDY CRITERIA

Prior to removal from study, effort must be made to have all subjects complete a safety visit approximately 30 days following the last dose of study therapy.

3.8.1 Criteria for removal from protocol therapy

- Completion of 6-month course of protocol therapy and no response (PR or CR)
- Chronic GvHD progression by NIH criteria and/or primary physician determination
- Unacceptable toxicity that requires the subject to be off study drug for more than 28 consecutive days in the first six months of the study
- Noncompliance with study medication (defined as missed >20% doses in the first six months of the study for the reason of noncompliance)
- If ibrutinib becomes unavailable
- Principal Investigator discretion
- Participant requested to be withdrawn from active therapy
- Recurrence of underlying malignancy
- Subject becomes pregnant

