6.3 RESPONSE CRITERIA

For the purposes of this study, participants should be evaluated for response at 6 weeks, 3, 6, 9 and 12 months from the start of ibrutinib by the bone marrow transplant physician and/or nurse practitioner trained in chronic GvHD assessments.

Chronic GvHD Organ Specific Staging and Global Scoring ([Appendix D](#) and [Appendix E](#)) will occur at screening and at 6 month visit, and will be repeated at 9 and 12 months. Response to treatment with ibrutinib will be assessed and documented in Chronic GvHD Activity Assessment (Clinician) Form A ([Appendix F](#)) at enrollment, 6 weeks and then 3, 6, 9 and 12 months from the start of ibrutinib. To ensure comparability, baseline and on-study methods for response assessment will be performed using identical grading, scale or techniques.

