6.3.1 Response Criteria

Efficacy will be assessed using NIH consensus criteria measuring for therapeutic response in clinical trials for chronic GvHD. The calculations for CR, PR and progressive disease are provided in [Appendix H](#).

- **CR** is defined as complete resolution in all of signs and symptoms at all affected organs or tissues.
- **PR** is defined as improvement in ≥ 1 organ or tissue with no progression in any other affected organ or tissue.
- **Stable Disease (SD)** is defined as no change in chronic GvHD.
- **Flare** is defined as exacerbation of chronic GvHD manifestations during withdrawal of immunosuppressive therapy which do not exceed those at the beginning of the trial and improves after reinstatement of previous treatment. For the purpose of this study, any flare which requires change or intensification of systemic therapy beyond the one per protocol allowed steroid pulse within initial four weeks will be considered a therapy failure.
- **Progressive disease (PD)** is defined as failure of therapy to control chronic GvHD. Participants who progress prior to 6 months evaluation will be also evaluable for the primary efficacy endpoint.
- **Mixed response** is defined as an improvement in some organs but worsening in others and will be categorized as progressive disease.

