16.8 APPENDIX H: RESPONSE DETERMINATION FOR CHRONIC GVHD TRIALS BASED ON CLINICIAN ASSESSMENTS

Organ	Complete Response	Partial Response	Progression
Skin	NIH Skin Score 0 after previous involvement	Decrease NIH Skin Score by 1 or more points	Increase in NIH Skin Score by 1 or more points, except 0 to 1
Eyes	NIH Eye Score 0 after previous involvement	Decrease in NIH Eye Score by 1 or more points	Increase in NIH Eye Score by 1 or more points, except 0 to 1
Mouth	NIH Modified OMRS 0 after previous involvement	Decrease in NIH Modified OMRS of 2 or more points	Increase in NIH Modified OMRS of 2 or more points
Esophagus	NIH Esophagus Score 0 after previous involvement	Decrease in NIH Esophagus Score by 1 or more points	Increase in NIH Esophagus Score by 1 or more points, except 0 to 1
Upper GI	NIH Upper GI Score 0 after previous involvement	Decrease in NIH Upper GI Score or more points	Increase in NIH Upper GI Score by 1 or more points, except 0 to 1
Lower GI	NIH Lower GI Score 0 after previous involvement	Decrease in NIH Lower GI Score by 1 or more points	Increase in NIH Lower GI Score by 1 or more points, except from 0 to 1
Liver	Normal ALT, alkaline phosphatase, and Total bilirubin after previous elevation of 1 or more	Decrease by 50%	Increase by 2 x ULN
Lungs	
 – Normal %FEV1, alkaline phosphatase, and Total bilirubin after previous elevation of 1 or more – If PFTs not available, NIH Lung Symptom Score 0 after previous involvement 	
 – Increase by 10% predicted absolute value of %FEV1 – If PFTs not available, decrease in NIH Lung Symptom Score by 1 or more points 	
 – Decrease by 10% predicted absolute value of %FEV1 – If PFTs not available, increase in NIH Lung Symptom Score by 1 or more points, except 0 to 1
Joints and fascia	Both NIH Joint and Fascia Score 0 and P-ROM score 25 after previous involvement by at least 1 measure	Decrease in NIH Joint and Fascia Score by 1 or more points or increase in P-ROM score by 1 point for any site	Increase in NIH Joint and Fascia Score by 1 or more points or decrease in P-ROM score by 1 point for any site
Global	Clinician overall severity score 0	Clinician overall severity score decreases by 2 or more points on a 0-10 scale	Clinician overall severity score increases by 2 or more points on a 0-10 scale

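### A participant with an early partial response who is then removed for progression before month 6 is never declared a non-responder, and 10.2 lets the early response count

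*Combined protocol and SAP*

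**What the plan says.** **Removal.** Section 3.8.1 lists, among the reasons to stop protocol therapy, "Chronic GvHD progression by NIH criteria and/or primary physician determination". The and/or allows the physician's judgement to be enough without progression by NIH criteria.

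**Progression for the endpoint.** In 6.3.1 progressive disease "is defined as failure of therapy to control chronic GvHD". The same section says "The calculations for CR, PR and progressive disease are provided in" Appendix H. That appendix sets thresholds organ by organ and adds a Global row: "Clinician overall severity score increases by 2 or more points on a 0-10 scale". Under 6.3, response is evaluated at 6 weeks and at 3, 6, 9 and 12 months, "by the bone marrow transplant physician and/or nurse practitioner trained in chronic GvHD assessments".

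**Early progressors.** Section 6.3.1 adds: "Participants who progress prior to 6 months evaluation will be also evaluable for the primary efficacy endpoint".

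**Failure rules.** Section 3.1 says: "Addition of any systemic immunosuppressive therapy aimed at controlling chronic GvHD symptoms is prohibited and will be considered treatment failure". Section 6.3.1 counts as therapy failure "any flare which requires change or intensification of systemic therapy beyond the one per protocol allowed steroid pulse" in the first four weeks.

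**Endpoint timing.** The primary objective (1.1.1), the stage-1 rule in 3.1 and the endpoint in 10.1.1 all refer to CR or PR at 6 months. Section 10.2, which contains the decision rule, refers to response at or before 6 months. Both 3.1 and 10.2 say that it may take 3 to 6 months to determine whether a subject has responded.

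**Denominator.** Section 10.4.2 uses evaluable participants and does not define the term. Section 10.3 reports on everyone who received at least one dose. Section 10.4.4 defines evaluability for safety only. Section 10.2 allows for 3 inevaluable participants.

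**The concern.** The trial's conclusion rests on one count in one arm, with cut-offs of 4 of 14 and then 8 of 25. A participant who improves at 6 weeks or 3 months and is then taken off because the disease has progressed is a failure of the treatment at month 6. The plan should give that participant one classification, and it does not. The sentence in 6.3.1 settles whether the participant is in the denominator but not whether he or she is in the numerator. The timing wording in 10.2 then lets the earlier response stand.

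The physician-determined route adds a second ambiguity. If the judgement is not matched by an Appendix H change, the record may show a partial response and no scored progression. Both ways of resolving the gap other than non-response (keeping the early response, or setting the participant aside as inevaluable and replacing him or her) raise the response rate. The first also affects the stage-1 decision to continue accrual.

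**Working it through.** **1. Tracing one participant.** Suppose a partial response on Form A at 3 months and removal for progression at month 4.

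| Question | Text | Answer |
|---|---|---|
| Is removal allowed? | 3.8.1 | Yes, by either route |
| Evaluable? | 6.3.1 | Yes, if the participant has progressed |
| Progressive disease, if judged by the physician without an Appendix H change? | 6.3.1, Appendix H | Not stated; the verbal definition would cover it, the calculation would not |
| Non-responder at 6 months? | 1.1.1, 3.1, 10.1.1 | Implied, not stated |
| Responder at or before 6 months? | 10.2 | Yes, on the 3-month assessment |

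The last two rows conflict. They conflict equally for progression by NIH criteria, so the numerator problem does not depend on the physician route. Nothing asks for a Form A when the decision to stop is made: footnote 9 of the study calendar lists only day 1, 6 weeks, and 3, 6, 9 and 12 months.

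**2. Reproducing the design.** Inputs from 10.2: 14 participants in stage 1, stop at 0 to 3 responses; 25 in total, positive at 8 or more; p0 = 0.20, p1 = 0.45.

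P(positive) = sum over x = 4 to 14 of P(Bin(14, p) = x) × P(Bin(11, p) ≥ 8 − x).

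At p = 0.20:
- x = 4: 0.1720 × 0.1611 = 0.0277
- x = 5: 0.0860 × 0.3826 = 0.0329
- x = 6: 0.0322 × 0.6779 = 0.0219
- x = 7: 0.0092 × 0.9141 = 0.0084
- x ≥ 8: 0.0024

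The sum is 0.0933, within the stated 0.10. Early termination is P(Bin(14, 0.20) ≤ 3) = 0.698, which matches the plan's 69.8%. At p = 0.45 the power is 0.903.

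**3. Early responses kept after progression.** Assume that the true 6-month rate is 20% and that a further 4% of participants (on average 1 in 25) keep an early response after progressing. The counted rate is 0.20 + 0.04 = 0.24. The same formula gives 0.0554 + 0.0692 + 0.0499 + 0.0219 + 0.0079 = 0.204. Early termination falls from 0.698 to 0.557.

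At the boundary, 7/25 = 28% is negative, and one retained response makes it 8/25 = 32%, which is positive. In stage 1, one retained response turns 3 of 14 (stop) into 4 of 14 (continue).

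**4. Failures set aside and replaced.** If k non-responders are replaced for every 25 counted, the counted rate is 0.20 × (25 + k)/25.

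| k | Counted rate | Type I error |
|---|---|---|
| 0 | 0.200 | 0.093 |
| 1 | 0.208 | 0.112 |
| 2 | 0.216 | 0.132 |
| 3 | 0.224 | 0.154 |

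The top of this range uses the whole allowance of 3 inevaluable participants in 10.2. The documents do not say that the allowance is meant for such cases, and they give no frequency for either path.

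**The case against.** **The sections can be read together.** The 6.3.1 wording for progressive disease is broad, and the Appendix H Global row is itself a clinician's judgement. On that reading, someone removed for progression under 3.8.1 has progressed and stays evaluable. This stands in part. A reader might infer that progression for the endpoint is defined by organ scores alone, or that a physician-determined progression is not progressive disease. The documents support neither. They leave open only what happens when the judgement does not reach an Appendix H threshold.

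**Exclusion runs against the text.** A reader might infer that the plan lets these participants be dropped. Section 6.3.1 keeps early progressors evaluable and 10.3 covers everyone dosed. Exclusion is possible only because evaluable is undefined in 10.4.2, which is a general gap and not a consequence of 3.8.1. This stands, so exclusion is the lesser part of the point.

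**The failure rules already catch many cases.** Anyone whose progression leads to added systemic immunosuppression is a treatment failure under 3.1 and 4.1.1. True, but those rules are triggered by the added or intensified therapy and not by the decision to stop, and no sentence equates treatment failure with non-response on the primary endpoint.

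**The early-response problem is one of timing.** If response by 6 months were the intended endpoint, an early partial response would be a proper success and 0.204 would not be an error rate. This is fair as logic. But the objective, the stage-1 rule in 3.1 and the endpoint statement all say at 6 months, and only 10.2 differs. Correcting 10.2 alone would remove most of the risk; it would still leave the physician-only removal without a category.

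**Conclusion.** The concern holds in a limited form. The plan keeps participants who progress before the 6-month evaluation in the denominator, does not make them non-responders, and in 10.2 uses a timing under which an earlier response can still count. This applies to both removal routes in 3.8.1 and to both the stage-1 and final counts, and its direction is upward. A second, smaller gap is that physician-determined progression short of Appendix H has no stated category. Replacement as inevaluable is possible only through the undefined denominator.

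The size is not known. Type I error is 0.093 as designed, 0.204 if the counted rate rises from 20% to 24%, and 0.112 to 0.154 if 1 to 3 failures are replaced. These results assume that the true 6-month rate is 20%, that the cut-offs are unchanged, and frequencies that do not come from the documents. They show that a single participant can matter in a trial of 25; they do not forecast what will happen. The design itself reproduces and is sound.

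**What to change.** Add to 6.3.1 and 10.4.2: a participant removed from therapy for chronic GvHD progression under 3.8.1 before the 6-month evaluation, whether by NIH criteria or by physician determination, is evaluable and a non-responder for the primary endpoint and for the stage-1 count, whatever response was recorded earlier.

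Change 10.2 to response at 6 months, in line with 1.1.1, 3.1 and 10.1.1. Report how many progressions were physician-determined only, so that readers can see how much the result depends on them.

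The removal criterion, the sample size and the cut-offs do not change, and the design's error rates (0.093 and power 0.903) then apply to the endpoint as the objective states it. The cost is a few sentences and one line in the report. The downside is that the reported rate may be slightly lower, because some physician-judged progressions might not have met Appendix H.
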